### **11.2 Potential Benefits to Others**

Currently in the literature there is no consensus as to the right way to diagnose a nerve with ambiguous continuity. There is agreement that patients must wait until EDX studies become sensitive, but even within the literature, the time for the first use of this test varies from three to eight weeks with most practitioners agreeing with a standard six week first EDX study. The current evidence is not sufficient to support the routine use of surgical exploration or watch-and-wait strategies for these injuries. Practitioners simply choose which option for a nerve injury based on their clinical guess as to the status of the nerve. This strategy represents the alternative to participation.

We, therefore, propose to allow the current standard of care to be the alternative to participation. In this case, a patient would be treated as all patients with this injury and differs from trial patients only in the fact that trial patients may have more information about the state of their nerve with which to make a more informed treatment decision with their treating surgeon.

## **12.0 Sharing Results with Subjects**

The results of this study include both subjective and objective measures. It is impossible to hide the subjective measures from the patients given the nature of our measurements. We will prevent active discussion of objective measures until final follow up at 20 weeks. Patients will be free to use their subjective assessments of the return of function in their standard-of-care treatment decisions. We will not inform other physicians except at the express consent of patients to do so. Subjective responses to treatment can be discussed, again at the patient's request, with treating physicians before final follow up. Objective test results will not be discussed with treating physicians until 20 weeks, again, only with patient consent to do so. In cases where the patient's decision to seek further surgical exploration of an injured peripheral nerve based on subjective return of function (or lack of return) seems ill-advised to members of the study team, a patient conference will be arranged in conjunction with the ethicist and DSB. Such cases where the patient intends to monitor a nerve where our subjective findings suggest clear evidence that the nerve requires surgical exploration, are expected to be rare. Other such cases, where the patient intends to elect for surgical exploration of a nerve which is believed, based on the results of the study, to be in continuity, may be slightly more common. In both of these cases, the patient's decision in conjunction with the treating surgeon (who is purposefully excluded from the study team to avoid any conflicts) is held to be paramount. Conferences of the type described above will be held in selected cases where the evidence from the trial is deemed to be clearly in conflict with the decision taken by the patient – only to ensure adequate education, again with prior consultation with the DSB. Unblinding will be discussed at this time as well.

## **13.0 Subject Payment and/or Travel Reimbursements**

Subjects will be compensated \$80 after completion of Visit 1. This is based on the standard hourly rate (\$10 per hour). Subjects completing visit 1 in the CRC will be provided with a \$10 meal card. This will be done through Greenphire ClinCard.

## **14.0 Economic Burden to Subjects**

### **14.1 Costs**

The subject will not incur any additional costs as a result of participation in this study. The study drug and placebo will be provided to the subject at no charge. The subject or the subject's insurance will be responsible for all standard of care costs associated with treatment for the nerve injury. Testing completed in the CRC for visit 20 weeks will be covered by study funding and will not impact insurance coverage. The EDX testing done on visit 1 and 6, 12, and 18 weeks post injury are considered standard of care and will be charged to the subject's insurance accordingly.

### **14.2 Compensation for research-related injury**

It is the policy of the institution to provide neither financial compensation nor free medical treatment for research-related injury. In the event of injury resulting from this research, medical treatment is available but will be provided at the usual charge. Costs for the treatment of research-related injuries will be charged to subjects or their insurance carriers.

## 15.0 Resources Available

### 15.1 Facilities and locations

This research will be conducted at the Penn State Milton S. Hershey Medical Center. Specifically, the trial day (when patients are given 4AP or placebo and monitored) is conducted in the Penn State Hershey Clinical Research Center (<https://research.med.psu.edu/research-support/crc>). Patients will be followed in the Penn State Hershey Outpatient Clinics in both the Orthopaedic Surgery and Neurology Departments. No patients will be treated, seen or recruited at any site outside of the Penn State Hershey Facility.

### 15.2 Feasibility of recruiting the required number of subjects

We have undertaken several different forms of analysis aimed assessing the feasibility of this study. These efforts combine in-depth studies of patient selection, sources, availability and estimates of the likelihood of recruitment if a patient is found.

**Patient Selection:** Patients eligible for this trial must exhibit the loss of nerve function from recent trauma or post-operative state (within 7 days of injury) where the state of nerve continuity is unknown. These patients do not currently qualify for objective EDX because of known limitations of that electrophysiologic testing. We will, as part of the trial perform these tests nonetheless to ensure that they are still not usable with and without 4AP treatment. Patients may have multiple nerves effected with at least one, defined and EDX testable nerve among them. Patients must have a functional loss that they themselves can appreciate at the time of enrollment because some of the employed tests are subjective. Patients must report the capacity to use and sense with that nerve before trauma, and must be willing to undergo a test which may expose only some functions and not others (see below). Moreover, patients must be willing to have a test of a return of function which, in all likelihood will be fleeting – lasting only so long as the circulating level of 4AP, allows the impulse conduction in the traumatized nerve before being cleared and excreted.

**Patient Source:** Patients will come from two sources. The first will be traumatized patients presenting with nerve dysfunction. These patients often have concomitant orthopaedic injuries, which require stabilization. If the nerve was dysfunctional before intervention, then the patient will be included as a recruit for aim 1. The second source is patients who suffer nerve dysfunction after a surgery or intervention where nerve injury may not have been expected, as is the case with routine fracture fixation or joint arthroplasty procedures. In such cases, post-intervention examination may reveal a loss of nerve function where the continuity of the nerve again cannot be established. These patients, owing to their intact nerve function before the intervention, will be included as recruits to aim 2. In point of fact, both groups of patients have the same phenotypic condition, namely the loss of nerve function where the continuity of the nerve is not demonstrable. However, they are grouped into differing aims because the latter group suffers nerve dysfunction as the result of an intervention or surgical procedure and critically, these patients will have a clear pre-intervention examination without any nerve dysfunction.

Splitting aims is necessary because of the differing means by which the patient is injured and the different circumstances of injury. Surgeons will often tell patients who would qualify for aim 2 that they are absolutely sure that the nerve is not severed, altering the pre-test/pre-trial likelihood that the patient may feel a return of function even if exposed to the placebo. We therefore intend to keep the recruitment and counselling of aim 2 patients separate from those who present after traumatic, non-iatrogenic nerve injury.

**Patient Selection and Availability Patient Availability and Cohort Query Analytics:** Ambiguous nerve continuity is common in our medical center. Initial estimates, based on stakeholder provider interviews,

indicate that there are sufficient cohorts to conduct this trial in our single institution with matched cohorts divided into sub-categories based on the extent of nerve involvement. Annually, presenting patients (aim 1) with nerve deficits and those whose nerve continuity becomes obscure after intervention (aim 2) number at least 24 and 50 respectively. Our proposed recruitment estimates, corrected for exclusion criteria and inability to consent, indicate that diagnostic trials on 4AP can be completed in 24 months with full follow up for our gold standard electrodiagnostic endpoint (10 weeks). Thus, within two years, we can answer this highly relevant clinical question unambiguously in our single center.

### **15.3 PI Time devoted to conducting the research**

[name] is allotted time to work on his research in agreement with his contract in the Department of Orthopaedics.

### **15.4 Availability of medical or psychological resources**

Medical or psychological care will be referred to resources here at Penn State Hershey Medical Center.

### **15.5 Process for informing Study Team**

As detailed in the team composition/budget justification, our team is composed of several different types of clinicians and scientists. This entire team will be housed at a single medical center (not at satellite facilities). In addition to quarterly meetings, the entire team will attend a yearly retreat to discuss issues surrounding this trial.

This communication time notwithstanding, the investigators will also communicate regularly, either by phone or in person, to discuss study progress, updates, and responsibilities. Communication will occur weekly during the first six months of the project to facilitate successful implementation of the project protocol. After six months, communication will be bi-weekly for the duration of the project period. Both investigators and the principal investigator will share their respective research results with key personnel. The study team will work together to discuss any changes in the direction of the research projects.

## **16.0 Other Approvals**

### **16.1 Other Approvals from External Entities**

Not applicable

### **16.2 Internal PSU Committee Approvals**

**Check all that apply:**

- Anatomic Pathology – Penn State Health only** – Research involves the collection of tissues or use of pathologic specimens. Upload a copy of “HRP-902 - Human Tissue For Research Form” in CATS IRB.
- Animal Care and Use – All campuses** – Human research involves animals and humans or the use of human tissues in animals
- Biosafety – All campuses** – Research involves biohazardous materials (human biological specimens in a PSU research lab, biological toxins, carcinogens, infectious agents, recombinant viruses or DNA or gene therapy).

- Clinical Laboratories – **Penn State Health only** – Collection, processing and/or storage of extra tubes of body fluid specimens for research purposes by the Clinical Laboratories; and/or use of body fluids that had been collected for clinical purposes but are no longer needed for clinical use. Upload a copy of “HRP-901 - Human Body Fluids for Research Form” in CATS IRB.
- Clinical Research Center (CRC) Advisory Committee – **All campuses** – Research involves the use of CRC services in any way.
- Conflict of Interest Review – **All campuses** – Research has one or more of study team members indicated as having a financial interest.
- Radiation Safety – **Penn State Health only** – Research involves research-related radiation procedures. All research involving radiation procedures (standard of care and/or research-related) must upload a copy of “HRP-903 - Radiation Review Form” in CATS IRB.
- IND/IDE Audit – **All campuses** – Research in which the PSU researcher holds the IND or IDE or intends to hold the IND or IDE.
- Scientific Review – **Penn State Health only** – All investigator-written research studies requiring review by the convened IRB must provide documentation of scientific review with the IRB submission. The scientific review requirement may be fulfilled by one of the following: (1) external peer-review process; (2) department/institute scientific review committee; or (3) scientific review by the Clinical Research Center Advisory committee. NOTE: Review by the Penn State Health Cancer Institute (PSCI) Protocol Review Committee or the PSCI Disease Team is required if the study involves cancer prevention studies or cancer patients, records and/or tissues. For more information about this requirement see the IRB website.

## 17.0 Multi-Site Study

- 17.1 Other sites**  
not applicable
- 17.2 Communication Plans**  
not applicable
- 17.3 Data Submission and Security Plan**  
not applicable
- 17.4 Subject Enrollment**  
not applicable
- 17.5 Reporting of Adverse Events and New Information**  
not applicable
- 17.6 Audit and Monitoring Plans**  
not applicable

## 18.0 Adverse Event Reporting

- 18.1 Adverse Event Definitions**

For drug studies, incorporate the following definitions into the below responses, as written:	
Adverse event	Any untoward medical occurrence associated with the use of the drug in humans, whether or not considered drug related
Adverse reaction	Any adverse event caused by a drug
Suspected adverse reaction	
Any adverse event for which there is a reasonable possibility that the drug caused the adverse event. Suspected adverse reaction implies a lesser degree of certainty about causality than “adverse reaction”.
 
 
• Reasonable possibility. For the purpose of IND safety reporting, “reasonable possibility” means there is evidence to suggest a causal relationship between the drug and the adverse event.
 

Serious adverse event or Serious suspected adverse reaction	
Serious adverse event or Serious suspected adverse reaction: An adverse event or suspected adverse reaction that in the view of either the investigator or sponsor, it results in any of the following outcomes: Death, a life-threatening adverse event, inpatient hospitalization or prolongation of existing hospitalization, a persistent or significant incapacity or substantial disruption of the ability to conduct normal life functions, or a congenital anomaly/birth defect. Important medical events that may not result in death, be life-threatening, or require hospitalization may be considered serious when, based upon appropriate medical judgment, they may jeopardize the patient or subject and may require medical or surgical intervention to prevent one of the outcomes listed in this definition.

Life-threatening adverse event or life-threatening suspected adverse reaction	
An adverse event or suspected adverse reaction is considered “life-threatening” if, in the view of either the Investigator (i.e., the study site principal investigator) or Sponsor, its occurrence places the patient or research subject at immediate risk of death. It does not include an adverse event or suspected adverse reaction that had it occurred in a more severe form, might have caused death.

Unexpected adverse event or Unexpected suspected adverse reaction.	
An adverse event or suspected adverse reaction is considered “unexpected” if it is not listed in the investigator brochure, general investigational plan, clinical protocol, or elsewhere in the current IND application; or is not listed at the specificity or severity that has been previously observed and/or specified.

For device studies, incorporate the following definitions into the below responses, as written:	
Unanticipated adverse device effect	
Any serious adverse effect on health or safety or any life-threatening problem or death caused by, or associated with, a device, if that effect, problem, or death was not previously identified in nature, severity, or degree of incidence in the investigational plan or IDE application (including a supplementary plan or application), or any other unanticipated serious problem associated with a device that relates to the rights, safety, or welfare of subjects.

## 18.2 Recording of Adverse Events

Adverse events will be assessed at every visit after consent is obtained.

All adverse events (serious or non-serious) and abnormal test findings observed or reported to study team believed to be associated with the study drug(s) or device(s) will be followed until the event (or its sequelae) or the abnormal test finding resolves or stabilizes at a level acceptable to the investigator.

An abnormal test finding will be classified as an adverse event if one or more of the following criteria are met:

- The test finding is accompanied by clinical symptoms

- The test finding necessitates additional diagnostic evaluation(s) or medical/surgical intervention; including significant additional concomitant drug treatment or other therapy

**NOTE:** Simply repeating a test finding, in the absence of any of the other listed criteria, does not constitute an adverse event.

- The test finding leads to a change in study drug dosing or discontinuation of subject participation in the clinical research study

The test finding is considered an adverse event by the investigator.

### **18.3 Causality and Severity Assessments**

The investigator will promptly review documented adverse events and abnormal test findings to determine 1) if the abnormal test finding should be classified as an adverse event; 2) if there is a reasonable possibility that the adverse event was caused by the study drug(s) or device(s); and 3) if the adverse event meets the criteria for a serious adverse event.

If the investigator's final determination of causality is "unknown and of questionable relationship to the study drug(s) or device(s)", the adverse event will be classified as associated with the use of the study drug(s) or device(s) for reporting purposes. If the investigator's final determination of causality is "unknown but not related to the study drug(s) or device(s)", this determination and the rationale for the determination will be documented in the respective subject's case history.

Data collected and events reviewed by [name] will also be reviewed by a non-conflicted investigator on the study.

### **18.4 Reporting of Adverse Reactions and Unanticipated Problems to the FDA**

#### **18.4. 1 Written IND/IDE Safety Reports**

The Sponsor-Investigator will submit a written IND Safety Report (i.e., completed FDA Form 3500A) to the responsible new drug review division of the FDA for any observed or volunteered adverse event that is determined to be a serious and unexpected, suspected adverse reaction. Each IND Safety Report will be prominently labeled, "IND Safety Report", and a copy will be provided to all participating investigators (if applicable) and sub-investigators.

Written IND Safety Reports will be submitted to the FDA as soon as possible and, in no event, later than 15 calendar days following the Sponsor-Investigator's receipt of the respective adverse event information and determination that it meets the respective criteria for reporting.

For each written IND Safety Report, the Sponsor-Investigator will identify all previously submitted IND Safety Reports that addressed a similar suspected adverse reaction experience and will provide an analysis of the significance of newly reported, suspected adverse reaction in light of the previous, similar report(s) or any other relevant information.

Relevant follow-up information to an IND Safety Report will be submitted to the applicable review division of the FDA as soon as the information is available and will be identified as such (i.e., "Follow-up IND Safety Report").

If the results of the Sponsor-Investigator's follow-up investigation show that an adverse event that was initially determined to not require a written IND Safety Report does, in fact, meet the requirements for reporting; the Sponsor-Investigator will submit a written IND Safety Report as soon as possible, but in no event later than 15 calendar days, after the determination was made.

#### **18.4. 2 Telephoned IND Safety Reports – Fatal or Life-threatening Suspected Adverse Reactions**

In addition to the subsequent submission of a written IND Safety Report (i.e., completed FDA Form 3500A), the Sponsor-Investigator will notify the responsible review division of the FDA by telephone or facsimile transmission of any unexpected, fatal or life-threatening suspected adverse reaction.

The telephone or facsimile transmission of applicable IND Safety Reports will be made as soon as possible but in no event later than 7 calendar days after the Sponsor-Investigator's receipt of the respective adverse event information and determination that it meets the respective criteria for reporting.

#### **18.5 Reporting Adverse Reactions and Unanticipated Problems to the Responsible IRB**

In accordance with applicable policies of The Pennsylvania State University Institutional Review Board (IRB), the investigator will report, to the IRB, any observed or reported harm (adverse event) experienced by a subject or other individual, which in the opinion of the investigator is determined to be (1) unexpected; and (2) probably related to the research procedures. Harms (adverse events) will be submitted to the IRB in accordance with the IRB policies and procedures.

#### **18.6 Unblinding Procedures**

In the case of a medical emergency the un-blinded IDS can disclose the randomization group. Contact information will be listed in the subject's electronic medical record (EMR). If such action is necessary, the Investigator and Safety Monitor will review the incident to determine if the subject should be withdrawn from the study. All emergency drug disclosures will also be reviewed at DSMC meetings to assure the continuing safety of research subjects.

#### **18.7 Stopping Rules**

Our safety analysis plan includes routine review (urgently within 48 hours) of every adverse event to the data safety monitoring board. The board will render a decision on suspension of the trial based on the available data in an unbiased manner. Examples of reasons for such a stoppage include adverse events that are not explainable, and patient dissatisfaction with the trial progression. The rules for stopping are not confined to adverse events, as defined by the drug information insert. The data safety monitoring board has the power to stop the trial for any reason surrounding safety, even if that includes investigating a particular patient's response to the trial drug or evaluation of the circulating levels of the drug at the time of an adverse event. Stopping rules include: Seizure, increased pain not treatable in the clinical research center, clear demonstration of a positive result which alters the statistical numbers for the trial, clear indications of deviations from the protocol, inadequate reporting by the trial team, and incomplete documentation of results.

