## **9.2 Data that are reviewed**

All clinical outcomes data will be reviewed.

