## **9.5 Individuals reviewing the data**

The Data Safety Monitoring Board will be reviewing the data a minimum of twice per year unless there is an adverse event reported and then a meeting will be convened to review the adverse event unless a meeting has already been scheduled within a week.

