## **9.7 Statistical tests**

Harm will be determined based on standard comparison of response to placebo with response to the drug. Each test, provided data from that test is normally distributed, which the data from each of our clinical and diagnostics are, is tabulated and compared with the same response when no active drug is in the system. Since all variables in our outcomes are continuous, the appropriate tests are standard t-tests. Theoretically, ordinal tests will be assayed with the chi-squared method.

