### **19.1. 2 Safety Monitoring**

A Data Safety Monitoring Board (DSMB) will be constructed of individuals with varying backgrounds to allow for a holistic approach to data monitoring. One of the goals will be to completely and comprehensively capture any adverse events and process information to the FDA and regulatory bodies at Penn State in a straightforward manner.

We intend to include an ethicist as a lay member of the DSMB as well as key members of the Clinical and Translational Science Institute (CTSI). The CTSI places the highest priority on ensuring the safety of patients participating in clinical trials. The initial review of trial protocol lies with the CTSI Scientific Review Committee (SRC) to ensure that the trial, regardless of sponsorship or support, contains adequate plans for data and safety monitoring. The CTSI is therefore a natural component of our Data and Safety Monitoring Board (DSMB), which will be responsible for monitoring this investigator-initiated trial (IIT).

The DSMB has the responsibility for continuing review and monitoring of the study. The DSMB's review and oversight are written in to the IRB-approved protocol for such trials. The DSMB provides oversight of study progress and safety by review of the following information:

- Rates of accrual and retention.
- Frequency and severity of adverse events (AEs) and serious adverse events (SAEs).
- Response rates, where appropriate.
- New information related to the trial, i.e., published scientific reports or other developments that may affect subject safety or ethical concerns.
- Any changes to the anticipated risk/benefit ratio of the study that would affect its continuation.
- Protocol deviations and violations (although this is the subject of independent audits by the IRB as well).
- Matters that pertain to serious errors or potential misconduct by any of the investigators or research staff, i.e., breaches in confidentiality, research fraud.
- Subject complaints.
- Conflicts of interest.

The DSMB will be empowered to recommend a halt of the study should there be deviations from established gender or race metrics of presenting patients in this "consecutive consent" design. The timeline for review of trials by the DSMB is determined at the outset of the study with approval by the SRC. The frequency of DSMB review required for this protocol at six

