months but will include an additional review after every ten patients recruited (whichever is most frequent). These details are recorded by the clinical coordinator, who prepares the skeleton of the report of the DSMB, which then adds the interpretation and evaluation sections of the report and then submits that to the IRB and study PI at least once yearly (but likely twice, depending on recruitment).

Roles in the reporting of adverse event(s) (AE(s)): The **Principal Investigator** will confirm that all adverse events (AE) are correctly entered into the AE case report forms by the coordinator; be available to answer any questions that the coordinators may have concerning AEs; and will notify the IRB, FDA, sponsor and/or DSMB of all applicable AEs as appropriate. All assessments of AEs will be made by a licensed medical professional who is an investigator on the research.

The **Research Coordinator** will complete the appropriate report form and logs; assist the PI to prepare reports and notify the IRB, FDA and/or DSMB of all Unanticipated Problems/SAE's.

The **Data Monitor** will confirm that the AEs are correctly entered into the case report forms. The Monitor will also confirm that the adverse events are consistent with the source documents and are reported to the appropriate regulatory bodies as required.

The ethicist will review every proposed consenting trial patient and report results monthly to the balance of the DSMB. Accrual will be monitored monthly by the DSMB based on this report.

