**Data Management and Monitoring:** Monthly monitoring by the co-investigator (from the Department of Public Health Sciences) will also be performed as per the mechanism offered by the Penn State Clinical Trial Data Management Center (housed within the same department). Trial outcome data will be held in a secure server within that department and an interim statistical analyses will be undertaken at the approximate midpoint for each specific aim (13 patients) via the Obrien-Fleming group sequential method to monitor the trial data. Early achievement of the trial result will be identified by this mechanism and written reports of progress towards this achievement will be relayed to the DSMB by this co-investigator. Quality control of serum data will be ensured through dual laboratory certification of serum results. The same control of clinical data will be ensured through dual independent assessment of each test on the patient during testing periods, and interpretation of EDX results by a qualified specialized blinded participating clinician. Analysis for any given patient's data will be contained to the timeline in Figure 2.

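### Does the positive-result item in section 18.7 allow an efficacy stop outside the O'Brien-Fleming look in section 19.1.2?

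*Combined protocol and SAP*

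**What the plan says.** Section 18.7 ends with a list of stopping rules. Between untreatable pain and protocol deviations stands "clear demonstration of a positive result which alters the statistical numbers for the trial". The item names no endpoint, limit, time or aim, and does not cite section 19.1.2.

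Section 19.1.2, in its paragraph on data management and monitoring, says that "interim statistical analyses will be undertaken at the approximate midpoint for each specific aim (13 patients) via the Obrien-Fleming group sequential method". It goes on: "Early achievement of the trial result will be identified by this mechanism". A co-investigator from Public Health Sciences reports progress in writing to the DSMB.

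The DSMB also meets on other occasions. Section 9.5 says "The Data Safety Monitoring Board will be reviewing the data a minimum of twice per year", and section 19.1.2 adds a review for each ten recruits. Its list of matters for review includes "Response rates, where appropriate". Section 9.2 states "All clinical outcomes data will be reviewed". Section 9.7 states "Harm will be determined based on standard comparison of response to placebo with response to the drug".

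**The concern.** A group sequential boundary holds its error rate only if efficacy is declared at the planned looks and the final test uses the matching critical value. Section 18.7 places a positive result beside items such as seizure, which can trigger at any time. It also says that its rules reach beyond adverse events. Neither section cites the other, and the DSMB has several meetings at which some outcome data are on the table.

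Read literally and in isolation, the item would let the board stop for efficacy at any meeting, on any standard of clear, without reference to the boundary. A positive claim from such a stop would carry a false-positive risk above the one that the O'Brien-Fleming look was chosen to protect.

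**Working it through.** **1. The planned look.** Inputs: 50 patients (8.1), two aims, 25-34 per aim (3.3.2), look at 13 (19.1.2). With an equal split, 50/2 = 25 per aim and 25/2 = 12.5, which rounds up to 13. The stated midpoint reproduces. At 34 per aim the midpoint would be 17, and 13 would be 13/34 = 38% of the information.

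**2. Can the boundary be supplied from what is written?** No alpha is stated, so I assume two-sided 0.05 per aim. The O'Brien-Fleming limits are |Z| >= c/sqrt(t) at the look and c at the end, with c solved from the bivariate normal (correlation sqrt(t)) so that the total crossing probability is 0.05.

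| Final n per aim | t | Look at 13 | Final |
|---|---|---|---|
| 25 | 13/25 = 0.52 | 1.980/sqrt(0.52) = 2.746, p <= 0.0060 | 1.980, p <= 0.0477 |
| 34 | 13/34 = 0.382 | 1.965/sqrt(0.382) = 3.178, p <= 0.0015 | 1.965, p <= 0.0494 |

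Once alpha and the statistic are chosen, the named method fixes the rest.

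**3. Which occasions carry an efficacy decision?**

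| Occasion | Section | Stated purpose | Efficacy test stated? |
|---|---|---|---|
| Look at 13 per aim | 19.1.2 | Early achievement of the result | Yes (O'Brien-Fleming) |
| Six-monthly and ten-patient DSMB reviews | 9.5, 9.6, 19.1.2 | Accrual, adverse events, deviations, complaints, response rates where appropriate | No |
| Drug-placebo comparison | 9.7 | Harm | No |

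Section 18.7 expresses the board's own power to stop in terms of safety. By-arm data at the ten-patient reviews are not stated anywhere. The two sections therefore fit together: 19.1.2 says how an early result is found and that the DSMB is told, and 18.7 lists such a result among the grounds on which the trial may stop.

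**4. Size if the literal reading were followed.** Assume by-arm data and an efficacy decision at every DSMB review, in addition to the two O'Brien-Fleming tests. The six-monthly schedule comes from even accrual over the 24 months in section 15.2: 25 x 6/24 = 6.25, then 12.5 and 18.75, so about 6, 12 and 19. Simulated type I error per aim at n = 25, Student's t-test:

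| Meaning of clear | Reviews at 10, 20 | Every five | At 6, 12, 19 |
|---|---|---|---|
| p<0.05 | 10.3% | 15.0% | 13.3% |
| p<0.01 | 5.8% | 6.8% | 6.4% |
| p<0.001 | 5.1-5.2% | 5.1-5.2% | 5.1-5.2% |

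The two planned tests alone give 5.1% in the same simulation. A normal approximation for the first two schedules gives 10.0% and 14.1% at p<0.05. At 34 per aim and p<0.05 the t-test gives 12.3% (reviews at 10, 20, 30), 17.7% (every five) and 13.1% (at 8, 17, 26).

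The every-five schedule needs equal accrual in the two aims. Section 15.2 gives at least 24 and 50 eligible presentations a year, so ten recruits would split about 10 x 24/74 = 3.2 and 6.8.

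For a yes/no endpoint at p<0.05, n = 25 and common true rates of 10-50%, the baseline matters:

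| Test | Two planned looks only | With the extra reviews |
|---|---|---|
| Uncorrected chi-squared | 1.8-5.2% | 2.6-15.1% |
| Fisher | 0.8-4.5% | 0.9-7.3% |
| Yates-corrected | 0.1-1.7% | 0.2-2.9% |

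Extra looks raise the rate under each test, but under Yates it stays below 5% because that test is conservative in small samples.

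**The case for a change.** The best case for a change is that the text never says that an early result may be identified only by the O'Brien-Fleming look. Section 18.7 speaks of the trial while 19.1.2 works by aim, so it is unclear whether a crossing in one aim stops that aim or both. The pilot label is not a full answer either: the sponsor chose an error-controlling method, states a hypothesis for each aim, and in section 15.2 expects an unambiguous answer. Adding a cross-reference would cost one line.

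Much of this is true as description. The cross-reference is missing, and alpha, the interim endpoint and test, the limits and the scope of a stop are not written down. But to infer from silence that a stop outside the boundary is allowed, one must add an efficacy test at meetings for which none is described, by-arm efficacy data that are not promised there, and a loose standard for a result that section 18.7 requires to be clear. The omitted details are ones that the biostatistician, who helped plan the trial and sits on the DSMB (8.3), must settle to run the interim analysis at all. A one-line link would tidy the text without altering any analysis that follows from it.

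**Conclusion.** No change is called for. Followed as written, early efficacy is judged by the O'Brien-Fleming look at 13 patients in each aim, and the item in 18.7 is most naturally read as the consequence of that look. What remains is missing detail that analysts fill sensibly.

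The inflation is conditional. It is about 10-15% per aim at 25 patients (12-18% at 34) if efficacy were tested by t-test at p<0.05 at every review, 5.8-6.8% at p<0.01 with 25 patients, and essentially nil at p<0.001. These figures rest on an assumed two-sided 5% alpha, by-arm data at each review and the accrual patterns above. The plan states none of the testing conditions. The study is a pilot meant to yield preliminary data (8.1), offers no formal sample-size basis (8.2) and sets no error rate for the loose wording to break.
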